## **XI. Setting up Blindness, Uncovering Blindness and Emergency Uncovering Blindness**

### **1. Blinding**

( 1 ) Subjects were randomly numbered and grouped : The cases were numbered

---

according to the time sequence of enrollment, and divided into three groups : A, B, and C. The patients were divided into three groups according to the time sequence of enrollment.

( 2 ) Randomly determined grouping : Randomly determined by drawing lots, group A, group B and group C correspond to ' experimental group ' or ' control group ', respectively.

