### **III.experimental design**

1. design description: A randomized, double-blind, parallel, placebo-controlled study.

2. technical route

---

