## **X. Statistical analysis of test data**

### **1. Data Selection for Statistical Analysis**

( 1 ) Full Analysis Set ( FAS ) : Constituted of all cases with depressive symptoms after papillary thyroid carcinoma surgery that were randomized into groups and at least 1 month after surgery, that is, Intention-to-treat. The FAS set was used for efficacy analysis, and the missing data was filled with the last observed data filling ( LOCF ) criterion.

( 2 ) Per-Protocol Set ( PPS ) : PPS is composed of all cases that meet the test plan, have good compliance, do not use prohibited drugs during the test, and complete the content of CRF requirements. The PPS set is used for efficacy analysis.

( 3 ) Safety Analysis Set ( SAS ) : It is composed of all cases that have been randomly grouped, used at least one drug and have safety evaluation. The SAS set is used for safety analysis.

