## 2. Provisions on Blinding

Uncover the blind bottom envelope : The three groups of A, B, and C are provided in the letter as test drugs or reference drugs. The groups corresponding to each number are assigned to statistical analysts for statistical analysis and statistical conclusions are made. According to the statistical conclusions, combined with professional knowledge, make professional conclusions.

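### Section XI.1 assigns patients to letters A, B and C by order of enrolment and draws lots only for what the letters mean, so it describes no patient-level randomisation

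*Combined protocol and SAP*

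**What the plan says.** Section III describes the study as "A randomized, double-blind, parallel, placebo-controlled study". Section X.1 builds on that label. The full analysis set, equated there with intention-to-treat, consists of cases "that were randomized into groups and at least 1 month after surgery", and of the safety set it says "It is composed of all cases that have been randomly grouped".

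The only account of how patients reach an arm is in section XI.1. Step (1) is headed "Subjects were randomly numbered and grouped". The sentences beneath it number cases in order of enrolment and divide them into A, B and C, and the rule is then repeated: "The patients were divided into three groups according to the time sequence of enrollment". Step (2) is where chance enters: "Randomly determined by drawing lots, group A, group B and group C correspond to" the experimental or the control group.

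Section XI.2 says of the blind-code envelope: "The three groups of A, B, and C are provided in the letter as test drugs or reference drugs". It adds: "The groups corresponding to each number are assigned to statistical analysts for statistical analysis". Section XI.3 refers to numbered emergency letters. Section 5.1 fixes the ratio at 2:1, with 200 experimental and 100 control patients. No section gives a random sequence, a block size or a means of concealing the next assignment. The technical-route figure in section III is not visible in the text available for review.

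**The concern.** Drawing lots for three letters randomises three labels, not 300 patients. Once enrolment order has fixed each patient's letter, everyone with that letter shares one draw. The procedure therefore conflicts with the randomised label in section III, with the analysis-set definitions in X.1 and with the heading of XI.1(1) itself.

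At stake is the basis for a causal comparison between the arms. If the letters are consecutive blocks of enrolment, the control group is a separate stretch of calendar time, and any drift in patients, raters or care is mixed with the treatment effect. None of the efficacy analyses in X.2(4) includes enrolment time. If the letters rotate, time is balanced, but the next letter is known in advance. The arm is then predictable as soon as a letter's meaning is learned or guessed.

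**Working it through.** **Inputs from the documents.** 300 patients, 200 experimental and 100 control (section 5.1); three letters (XI.1); significance at P ≤ 0.05 and a t test on score change (X.2); trial window 2023.3 to 2024.5 (XII); final visit at day 90 ± 3 (7.3).

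**Assumptions, because the documents give no figure.** Equal letters of 100; one lasting meaning per letter, as the XI.2 envelope implies; linear drift of *d* HAMD points in score change from first to last patient; SD of change 4 to 6; two-sided 5% test.

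**1. The plan's own split.** 300 × 2/3 = 200 and 300 × 1/3 = 100, which reproduces section 5.1. Over three equal letters this means two experimental and one control.

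**2. Number of possible allocations.** Choosing the control letter gives C(3,1) = 3. An individual 2:1 list with fixed totals has C(300,100), with log10 = 81.62, or about 4 × 10^81. Fresh lots for every three patients would give 3^100, about 5 × 10^47. A randomisation test on three equally likely draws cannot give p below 1/3; reaching 0.05 needs at least 1/0.05 = 20 outcomes.

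**3. Drift bias.** Scale enrolment position as x = (position − 1)/299.
- Consecutive thirds, control first: mean positions are 50.5 (control) and 200.5 (experimental), so the bias is 150/299 = 0.502*d*. Control last gives the same size with opposite sign. Control in the middle gives 150.5 against (50.5 + 250.5)/2 = 150.5, so zero.
- Rotation: mean positions of A, B and C are 149.5, 150.5 and 151.5. The largest difference is 151 − 149.5 = 1.5, so the bias is at most 1.5/299 = 0.005*d*, or 0.015 points at *d* = 3.

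**4. False-positive rate of the t test.** SE = SD × √(1/200 + 1/100), which is 0.490, 0.612 and 0.735 for SD 4, 5 and 6. With m = bias/SE, the rate is about Φ(−1.96 − m) + Φ(−1.96 + m). The tabled values also count within-arm drift in the pooled variance, which changes them little. Example, *d* = 1 and SD 5: m = 0.502/0.612 = 0.82, and Φ(−2.78) + Φ(−1.14) ≈ 0.13.

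Consecutive thirds, control first or last:

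| *d* | Bias (points) | SD 4 | SD 5 | SD 6 | Mean of all 3 draws, SD 5 |
|---|---|---|---|---|---|
| 0.5 | 0.25 | 8.0% | 6.9% | 6.3% | 6.3% |
| 1 | 0.50 | 17.6% | 12.9% | 10.5% | 10.3% |
| 2 | 1.00 | 53.2% | 37.2% | 27.5% | 26.4% |
| 3 | 1.51 | 86.4% | 68.7% | 53.2% | 47.4% |

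A simulation of 4,000 runs at SD 5 gave averages of 10.3%, 26.0% and 47.5% for *d* = 1, 2 and 3. With control in the middle, or under rotation, the rate is 4.5% to 5.0% over the range shown.

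**5. Time span of a letter.** 1 March 2023 to 31 May 2024 is 458 days. If the window includes follow-up, accrual is at most 458 − 90 = 368 days, and one of three consecutive letters spans at most 368/3 = 122.7 days, about 4 months.

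**6. Code-break exposure.** If the code shared by a letter is opened for one randomly chosen patient, it is control with probability 1/3, and then all 300 arms are known to anyone who knows the letters. With probability 2/3 it is experimental, and 100 arms are known. An individual code reveals one.

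**The case against.** The English is rough, and XI.1 may be a poor account of a sound scheme. The heading of step (1) says patients were randomly grouped, and XI.2 and XI.3 mention numbers that could be case-level codes. The text does not say how often lots were drawn, so the count of three rests on a single draw, equal letters and a fixed meaning per letter. This limits the claim to what the plan describes; it does not show that no random step was used. It does not remove the conflict, however. An envelope giving each letter one meaning speaks against repeated draws, and a numbered envelope is not a random sequence.

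The word parallel in section III fits rotation better than consecutive thirds, and rotation does almost no harm through drift. Nothing in the documents supports a drift of 1 to 3 points within about a year, and at 0.5 points the inflation is small. This stands: the larger error rates are conditional illustrations, not expected values. The 1/3 floor on a randomisation p-value shows how little chance enters, but the plan does not use such a test for efficacy.

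The code-break exposure is a vulnerability, not an expected loss. XI.3 restricts who may open a letter, nothing sends the result to the HAMD-24 raters, and labelling of packs by letter is not described.

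**Conclusion.** The concern holds, with high confidence, as a statement about the text, and it must be fixed. Section XI.1 describes allocation by enrolment order plus one group-level draw, and a trial run that way would not be individually randomised. This conclusion needs no assumed drift or SD; the count of three outcomes needs equal letters and one fixed meaning per letter.

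The size of the harm cannot be settled from the documents. Under rotation with an intact key there is no material drift bias, and the weakness is predictability. Under consecutive thirds, half of any linear drift goes into the treatment effect in two of three draws, and for assumed drifts of 0.5 to 3 points the error rate in those draws runs from 6.3% to 86.4%. A report could call the trial randomised at patient level only if the method actually used differs from this text.

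**What to change.** **If enrolment has already taken place** (section XII dates the trial from 2023.3): document the method actually used. State whether letters rotated or ran consecutively, how often lots were drawn, who held the key and how packs were labelled. If there was no patient-level random step, qualify the randomised description in sections III and X.1 and in the report. The cost is one documented description and matching wording.

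**If enrolment has not taken place:** replace XI.1 with a computer-generated, concealed, individual 2:1 list prepared by someone not involved in enrolment, with a unique kit number per patient and no shared letters. Delete the sentences that divide patients by time of enrolment. Add one sentence each to XI.2 and XI.3 stating that the numbers mentioned there refer to individual patients' treatments, so that an emergency letter reveals only that patient's arm. The cost is the wording, one list and individually numbered kit labels.

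In either case the sample size, the 2:1 ratio, the visits, the numbered emergency letters and the limits on opening them stay as they are.

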## 2. Provisions on Blinding

Uncover the blind bottom envelope : The three groups of A, B, and C are provided in the letter as test drugs or reference drugs. The groups corresponding to each number are assigned to statistical analysts for statistical analysis and statistical conclusions are made. According to the statistical conclusions, combined with professional knowledge, make professional conclusions.

## 3. Emergency Blinding

When the patient has serious adverse reactions or emergency events need to determine the group for treatment, when the patient has serious complications or symptoms of deterioration must take emergency measures, emergency cases do need to break the blind, by the researchers in the center of the person in charge, the person in charge after consultation with the bidding unit can read the emergency letter to break the blind. Once the corresponding numbered emergency letter is opened, the case is treated as a shedding case.

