##### ( 3 ) Drug source

---

The above drugs were produced and provided by Jinhua Shouxiangu Pharmaceutical Co., Ltd., and all research drug tests were qualified. If the drug expiration test is not completed, the drug needs to be re-prepared and blinded.

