### 5.5 Drug storage and recovery

The storage conditions of the drugs studied were : closed, placed in a clean, ventilated, shady place, away from children 's contact.

All test drugs must be stored safely and sealed, kept and distributed by a special person, and supervised the subjects to take them on time as required. The researcher should register and sign the medication record form after each administration to the patient, and be responsible for recycling the used test drug packaging bags.

Researchers and sponsor supervisors must count all drugs at the end of the trial and check with the number of drugs issued, the number of missing drugs and the cause of CRF. At the end of the trial, all unused drugs should be returned to the sponsor, and the relevant handover procedures and records should be completed according to GCP requirements.

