#### ( 3 ) Immune enhancement

## **IX.Evaluation of adverse events**

1.Definition of adverse events : Any disease that occurs during a drug clinical trial, new symptoms, signs or abnormal laboratory tests, or deterioration of the original symptoms and signs, whether or not related to the test drug, is an adverse event.

---

2. Relationship between adverse reactions and experimental drugs : Searching through the CNKI database, no side effects and related adverse reactions of Ganoderma lucidum were found in the current study. If complained of discomfort, through laboratory tests such as blood routine, liver and kidney function, platelets, hemoglobin, determine or determine whether it is related to the test drug.

3. Adverse event recording and reporting channels :

In the event of adverse events, the occurrence time, clinical manifestations, treatment process and duration, outcome and the relationship between the test drugs should be recorded in detail on the case report form page. Serious adverse events should fill in the serious adverse events form and report to SFDA Registry Drug Research and Supervision Office within 24 hours, notify the team leader unit and the bidder, and report to the center ethics committee, and submit details within 7 days thereafter.

Safety evaluation at the end of the trial should include all patients who have used the test drug, regardless of whether they meet the evaluable criteria.

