### **2. statistical analysis plan**

---

Statistical analysis was performed using SPSS 9.1.3 statistical software.

( 1 ) Distribution of two groups of cases : the comparison of the shedding and elimination rates of the two groups was performed by  $\chi^2$  test or exact probability method.

( 2 ) Comparability analysis : Demographic data and other basic indicators were compared to measure the comparability of the two groups. According to the type and distribution of data,  $\chi^2$  test or exact probability method, CMH test, t test, variance analysis or non-parametric statistical method were used.

( 3 ) Compliance analysis : To compare whether the two groups of patients use the test drugs on time and in quantity. The drugs that were not banned in the regimen were mainly tested by  $\chi^2$  test or exact probability method.

( 4 ) Validity analysis : Repeated measures were used to compare the differences in measurement data such as depression scores and sleep scores between the experimental group and the control group, or linear regression models were used to control baseline depression scores or sleep scores. Differences in depression scores and sleep scores between the two groups. Compare the score after the end of the experiment with the baseline score, calculate the difference before and after the change, and use the t test to compare the difference between the score changes of the experimental group and the control group.

( 5 ) Safety analysis : adverse reactions were statistically described, and the incidence of adverse reactions in the two groups was compared by  $\chi^2$  test or exact probability method.

( 6 ) All statistical tests should give test statistics and corresponding p values. When using the exact probability method, the p value is given directly.  $P \leq 0.05$  indicated that the difference was statistically significant.

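### Section XI.3 lets the emergency letter be read only after consultation with an outside party, with no exception for urgent cases, so access to the treatment code can be delayed

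*Combined protocol and SAP*

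**What the plan says.** Section XI.3 (Emergency Blinding) describes the situations in which a patient's code may be broken: serious adverse reactions or emergencies where the group has to be known for treatment, and also "when the patient has serious complications or symptoms of deterioration must take emergency measures". For all of them it sets one route. The matter goes to the person in charge at the centre, and then "the person in charge after consultation with the bidding unit can read the emergency letter to break the blind". The consequence of opening is stated next: "Once the corresponding numbered emergency letter is opened, the case is treated as a shedding case".

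The term 'bidding unit' is not defined. Section IX has a related term: for serious adverse events the centre must "notify the team leader unit and the bidder", in addition to reporting to the regulator and the ethics committee. Section 5.5 speaks of a sponsor: "all unused drugs should be returned to the sponsor".

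**The concern.** An emergency code break exists for the occasions when someone treating the patient cannot wait. Here access depends on first reaching and consulting a party outside the centre. If that party cannot be reached promptly, for instance at night or on a holiday, the person in charge must either wait or depart from the protocol. What is at stake is the safety of the individual patient. A second, lesser cost is that a centre which acts correctly under pressure would have a protocol deviation on record.

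**Working it through.** No formula applies and the plan gives no figure to reproduce. The check is to read XI.3 against every other section that might supply a faster route or a reason for the consultation.

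1. **Order of steps in XI.3.** The sentence is loosely built, but the order is clear: consultation precedes reading the letter. The same step applies to every situation listed, including those that call for emergency measures.

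2. **Safeguards within XI.3.** There is no carve-out for urgent cases, no limit on how long consultation may take, no round-the-clock contact and no instruction for when the other party cannot be reached.

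3. **Other routes.** XI.2 covers only the code break for the final analysis. Section IX covers the definition, recording and reporting of adverse events, with the regulator told of serious ones within 24 hours and details within 7 days. Section 4.4 lists reasons for withdrawal. None of them gives access to an individual patient's code, so XI.3 is the only emergency route.

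4. **Who is consulted.** Section IX treats the 'bidder' as a party to be told of serious events, separate from the regulator and the ethics committee. That fits a translation of 'sponsor', the word used in 5.5. The inference is sound, but the delay does not depend on it: a required consultation with any outside party has the same effect.

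5. **What prior consultation adds.** Section IX already has the bidder notified of serious adverse events. The documents give no further purpose that would require consultation to come first.

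6. **Size.** The expected number of delayed code breaks would be 300 patients × rate of code breaks × share delayed. The documents give neither of the last two. A rate of serious adverse events cannot stand in for the rate of code breaks, because XI.3 opens letters only where the blind needs to be broken, which is a subset. No count is therefore offered.

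7. **What opening a letter can reveal.** XI.1 and XI.2 use three group codes, A, B and C, and section 5.1 allocates 200 to active and 100 to placebo. Assume the three groups are of equal size: 300 / 3 = 100 per code. If a person who learns one patient's treatment also knows the group codes, the treatment of the other 100 − 1 = 99 patients with that code is revealed. If that code is placebo, the remaining 300 − 100 = 200 must all be active, and the whole trial is exposed. The documents do not say whether staff can see the codes, so this is conditional. It bears on how the fix is worded.

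**The case against.** The best defence is that XI.3 asks for consultation, not consent. The decision stays with the centre, and nothing tells staff to withhold care while they wait. A pause for consultation inside an emergency procedure may be undesirable, but it is not a contradiction in terms. With only three group codes, a check before opening might also protect the blind of other patients. And deletion is not the only repair: an exception for cases where the other party cannot be reached in time would meet the main worry.

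Much of this stands. The text creates a possible delay, not a demonstrated one, and the three-code design is a real reason to handle opened letters carefully. But that care can be taken by restricting who sees the result, without holding up the person who needs it. An exception limited to unreachable parties would be better than the present text, yet it would still ask the centre to judge reachability in the middle of an emergency.

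Two stronger readings are tempting. The first is that the sponsor can veto unblinding or choose which patients become shed. The text gives it consultation only, and nothing says the consulted party knows the treatment at that stage. The second is that opened cases drop out of the main analysis. Section X.1 builds the FAS from randomised cases, does not exclude shed ones, and says that "the missing data was filled with the last observed data filling ( LOCF ) criterion". Section IX keeps every patient who used the test drug in the safety evaluation. The shed label could affect the PPS, could lead to LOCF replacing later scores if follow-up stops, and enters X.2 (1), where "the comparison of the shedding and elimination rates of the two groups was performed by" a chi-square or exact test. Those effects come from the shed-on-opening rule, not from the consultation.

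**Conclusion.** The point holds as a matter of safety procedure. The only emergency route to the code requires prior consultation with an outside party and makes no exception for urgent cases, so following it as written can delay access. It should be corrected. Few patients are likely to be affected, though the documents give no rate, but the consequence for any one of them could be serious and the correction costs very little.

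The conclusion rests on the plain order of steps in XI.3 and on the absence of another route elsewhere in the documents. It does not rest on who the bidding unit is. A reader might infer that it is the manufacturer, with an interest in the product. The documents do not go that far: the drug source entry under 5.2 says "The above drugs were produced and provided by" a named company, but does not call that company the sponsor. Nor do the documents support a claim of sponsor control over unblinding, of bias in the FAS, or of any particular number of delayed code breaks.

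**What to change.** In XI.3, remove prior consultation as a condition for opening the letter. The replacement should say that:

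- the centre's person in charge may open the single patient's emergency letter when the emergency requires the treatment to be known;
- the time and reason are recorded;
- the bidding unit is notified afterwards, without the treatment or group code being stated;
- the opened result is given only to those who need it to care for that patient, and is kept from other trial staff.

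The term 'bidding unit' should be defined, or replaced by the word used in 5.5 if the sponsor is meant.

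The cost is a short change to one section. The outside party loses prior sight of code breaks; the recorded reason and the later notice largely make up for this, and section IX already has the bidder told of serious adverse events. The last bullet is needed because of the three shared codes: without it, one opened letter could reveal the arm of other patients with the same code. The change affects neither the sample size nor the analysis.

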### **V.test scheme**

#### 5.1 Number of cases and distribution of cases

According to the ' Drug Registration Management Method ', the study sample should be no less than 100 pairs. It is assumed that the case shedding rate is 15 %, and the sample size is not less than 117 pairs. Finally, the sample size was determined to be 300 cases. In order to reduce the use of placebo in the control group, so that more patients benefit from treatment, the experimental group : the control group was assigned to 2 : 1, that is, 200 cases in the experimental group and 100 cases in the control group.

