### 7.4 Principles of index collection

( 1 ) Hamilton Depression Scale ( HAMD-24 ) score and Pittsburgh Sleep Quality Index score :

The HAMD-24 was evaluated by two senior clinical psychologists, who were responsible for the assessment of HAMD-24 by [name]. PSQI was evaluated by

---

the subjects themselves and guided by psychologists.

(2) Fecal sample collection method :

①The stool collector was placed in the toilet, the feces were discharged into the collector, and the fresh fecal samples were fully mixed with a slender handle spoon ( Note : to avoid urine contaminated feces ).

②The mixed fecal samples were divided into two 5 ~ 10 mL sterile tubes marked with good names or pre-sterilized collection tubes, and about 2 ~ 3 mL of each tube was collected.

③About 1 ml fecal samples were sub-packed into 1.5 ml centrifuge tubes from 5-10 ml sample collection tubes with long-stem wooden rods. Or take about 1 ml to 1.5 ml centrifuge tube directly from the mixed fecal samples in 1.

④The centrifuge tube was covered well, and the fit was checked. According to the numbering order, it was placed in the sample box and placed in a refrigerator at -80 ° C for cryopreservation.

If the feces are collected at home, the collection tube is packed with a self-sealing bag and sent to the hospital sample receiving place as soon as possible ( within two hours ).

Notes for sample collection and preservation :

Samples should not be exposed to room temperature for more than 2 hours.

Sample collection should be carried out at the same time of the day to avoid the influence of rhythm on metabolism.

The sample should be mixed immediately after collection, and frozen after separation.

Prepare two samples at the same time to avoid repeated freezing and thawing.

(3) Blood sample collection:

①The remaining venous blood after thyroid function test in the laboratory was injected into the serum / plasma separation tube, and mixed upside down for 5-8 times.

②The whole blood was placed at room temperature ( 20 ° C ~ 25 ° C ), standing for about 30min ( no more than 2h ), and the blood was completely solidified,

---

and the anticoagulant was added as plasma.

③ After the serum / plasma was fully separated, centrifuged at 1000 g for 10 min. About 500  $\mu$  l-1mL of the supernatant was taken to a 1.5mL centrifuge tube ( recommended multi-tube subpackage ) and placed in a cryopreservation box.

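### One emergency unblinding can disclose a whole group, or the whole trial, to anyone who can work out the group letters; HAMD-24 raters are not shielded, and the opened case may lose her D90 score

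*Combined protocol and SAP*

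**What the plan says.** In what follows, 'letter' means the group code A, B or C, and 'envelope' means the sealed emergency document.

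- **Design (III).** The trial is described as "A randomized, double-blind, parallel, placebo-controlled study". Section I says that it runs at one institution only.
- **Size (5.1).** Allocation is 2:1, giving "200 cases in the experimental group and 100 cases in the control group".
- **Coding (XI.1).** Cases are numbered "according to the time sequence of enrollment, and divided into three groups : A, B, and C". The treatment meaning is then attached to the letter and not to the patient: "Randomly determined by drawing lots, group A, group B and group C correspond to ' experimental group ' or ' control group ', respectively".
- **End-of-trial unblinding (XI.2).** "The three groups of A, B, and C are provided in the letter as test drugs or reference drugs". The link from patient number to group is mentioned only as something handed to the statistical analysts.
- **Emergency unblinding (XI.3).** The person in charge at the centre may open the envelope after consulting the bidding unit, when a serious reaction, complication, deterioration or other emergency makes it necessary. Then: "Once the corresponding numbered emergency letter is opened, the case is treated as a shedding case".
- **Outcome assessment (7.4).** "The HAMD-24 was evaluated by two senior clinical psychologists". PSQI is completed by the patient with a psychologist's guidance.
- **Analysis sets (X.1).** The FAS is all randomised cases at least one month after surgery. It is called intention-to-treat, and missing values are filled by LOCF. The PPS requires good compliance and complete CRF content. Sections IX and X.1 keep treated patients in the safety evaluation.

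**The concern.** Where treatment is coded patient by patient, opening one envelope costs the blind for one patient. Here the code has only three values, so one patient's treatment together with her letter gives the treatment of everyone who shares the letter. If she is control, the other two letters must both be experimental and nothing remains hidden.

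The letters follow enrolment order, and a single enrolling site knows that order. The leading indicator is an observer-rated scale, so a rater who learns the code could, without intending to, shift the between-arm difference. Section XI places no barrier between the person who opens an envelope and the psychologists who rate.

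The second issue is what happens to the opened case. She is opened because something has gone wrong, and that can be related to outcome. If being classed as shed means that her D90 assessment is not done, her final score is missing for a reason that may be informative.

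**Working it through.** **The plan's own figure on shedding.** Section 5.1 starts from 100 pairs and allows 15% shedding: 100 / (1 − 0.15) = 117.65. The plan states not less than 117 (118 if rounded up). The figure reproduces and is not in dispute.

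**Letters and sizes.** A 200:100 split over three letters implies two experimental letters and one control. Lots decide which letter is control. For the experimental total to be 200 whichever letter is drawn, each letter must hold 300 − 200 = 100 patients. The plan does not state the letter sizes, so equal letters is an inference.

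**What one opening discloses.** Assume that letters are knowable at the site, that each has 100 patients, and that an opening is equally likely in each.

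| Opened case | Probability | Disclosed with certainty | Other letters |
|---|---|---|---|
| Control | 1/3 | 300 of 300 | both known to be experimental |
| Experimental | 2/3 | 100 of 300 | odds of experimental for each fall from 2:1 to 1:1 |

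**Several openings.** The code stays partly hidden only if all k openings fall in the same experimental letter, which has probability 2 × (1/3)^k. So P(whole trial disclosed) = 1 − 2 × (1/3)^k:

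- k = 1: 1 − 2/3 = 33.3%
- k = 2: 1 − 2/9 = 77.8%
- k = 3: 1 − 2/27 = 92.6%

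With patient-level codes that cannot be derived from enrolment order, k openings disclose k patients.

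**Ratings at risk.** Only assessments made after the opening can be affected. If f is the fraction of disclosed patients whose D90 rating is still to come, the D90 ratings at risk number 100f or 300f. The documents give neither f nor the probability of any opening. Section IX reports that a literature search found no adverse reactions to the product, so openings may be few.

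**The opened case, section by section.**

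- XI.3 makes her a shed case but names no analysis set and does not say whether assessments stop.
- X.1 keeps her in the FAS, because she was randomised, and fills a missing D90 score by LOCF. If the opening comes after D28, the D28 score is carried forward. If it comes before D28, the baseline score is carried forward and her recorded change is zero by construction. A patient who had worsened would then be recorded with an earlier, better score.
- The PPS definition probably excludes her.
- Section 4.3(3) can be read as rejecting cases with withdrawal or missing main indicators, which conflicts with an intention-to-treat FAS.
- Section 4.4(2) separately withdraws patients with severe adverse reactions, so many opened cases may leave by that route as well.

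**The case against.** The strongest reply is that the step from one envelope to a whole group is not written in the plan. The envelope is numbered, which reads as one per case. XI.2 gives the number-to-group link only to the analysts. Nothing says that site staff, dispensers or raters see a letter, and no rule turning enrolment order into A, B or C is given. This stands: disclosure is conditional on the letters being known or inferable. It does not remove the concern, because number and letter both come from an order that the site knows, and no section withholds the letters.

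A reader might infer that HAMD-24 has therefore lost its blind. The documents do not support that. The person in charge reads the envelope, and nothing says that the psychologists are told. What can be shown is that no barrier is stated. PSQI is less exposed, since it is self-rated, although with guidance, and site knowledge does not by itself unblind patients.

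A reader might also infer that opened cases are dropped from the analysis. X.1 keeps them in the FAS, the safety evaluation covers them, and X.2(1) compares shedding rates between groups. Nor does XI.3 say that D90 collection ceases, and an opened case need not be one whose depression has worsened. What remains is the risk that D90 is not collected and LOCF fills it.

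Finally, averaging the two outcomes gives (1/3) × 300 + (2/3) × 100 = 166.7 patients per opening. That should not be read as the number of compromised ratings: it rests on all three assumptions above and counts patients already past D90.

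**Conclusion.** The point holds as a conditional risk that the plan leaves uncontrolled. Tying treatment to three letters means that one emergency opening can disclose far more than one patient. Given knowable, equal-sized letters and equally likely openings, there is a 1/3 chance of disclosing all 300 patients and a 2/3 chance of disclosing about 100. None of these three conditions is stated in the documents. Only ratings made after the opening are exposed, and the shift in HAMD-24 that might follow cannot be estimated from the plan.

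The treatment of the opened case is a separate, smaller defect. She remains in the FAS and in the safety evaluation, but her D90 score may be replaced by LOCF for a reason that can be linked to outcome, and she probably leaves the PPS. Sections 4.3, 4.4, X.1 and XI.3 do not agree on her status and must be reconciled.

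**What to change.** 1. **Coding (XI.1, XI.2).** Use a patient-level randomisation list, with unique kit and emergency-envelope codes that cannot be derived from enrolment order, so that one envelope discloses one patient. Hiding the letters is not enough: if they follow enrolment order, the site can still work them out from the patient numbers.
2. **Raters (7.4, XI.3).** State that the HAMD-24 raters are not told of any opening or of its result.
3. **Opened cases (XI.3).** Replace the last sentence with: *The unblinding is recorded; the patient stays in the FAS, and her remaining D28 and D90 HAMD-24 and PSQI assessments are still collected where she consents, whether or not study drug continues.*
4. **Consistency.** Reconcile 4.3, 4.4 and X.1 with that sentence, and say whether an opened case belongs to the PPS.

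Cost: a new randomisation list, relabelling of kits and envelopes, wording changes, and some follow-up of opened cases at visits already scheduled. No new visits are needed.
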